10.3. Archival Tumor Tissue

If available, archival tumor tissue (eg, block or slides) will be collected and banked for assessment of relevant DNA, RNA, and protein markers, such as those involved in the CDK4/6 pathway. For additional guidance, please refer to the Laboratory Manual.

10.4. Optional Tumor Biopsy at Time of Disease Progression

Optional fresh tumor biopsies at the time of disease progression may be collected and banked for analysis of relevant DNA, RNA, and protein markers, such as those involved in resistance pathways. For additional guidance, please refer to the Laboratory Manual.

10.5. Pharmacokinetic Assessments

10.5.1. Pharmacokinetic Sampling

Blood samples for measurement of G1T38 and osimertinib concentrations will be collected as described below and outlined in Table 9-1 (Part 1) and Table 9-2 (Part 2). Information on blood sample collection, handling and storage can be found in the Laboratory Manual.

Part 1

Serial PK blood samples for the measurement of G1T38 concentration in plasma will be collected from all patients in Part 1 on Cycle 1 Day -16 and Cycle 1 Day -2 as outlined in Table 10-2. G1T38 must be administered by clinic staff on Cycle 1 Day -16 and Cycle 1 Day -2.

Pharmacokinetic blood samples for the measurement of osimertinib trough concentration and the G1T38 pre-dose concentration in plasma will be collected from all patients in Part 1 on Cycle 1 Day -2. These samples should be taken **prior to** (within 60 minutes) the morning dose of osimertinib and G1T38. The doses of G1T38 and osimertinib should be taken together, but G1T38 may be given up to 60 minutes after the osimertinib dose.

The actual times of blood sample collections should be documented in the eCRF.

Table 10-2 Part 1: Cycle 1 Day -16 and Cycle 1 Day -2 Blood Sampling Scheme

		Time P	oint (h) Rela	ative to G1T.	38 dose on	Cycle 1 Da	ay -16 and	on Cyc	ele 1 Da	ıy -2
Sample	0 (Pre- dose)	1	2	3	4	6	8	24	32	48
Window	-60 minutes		(± 10 minute	es)	(±	= 20 minute	(± 3 hours ^a)			

h = hour

Actual times will be recorded in the eCRF.

a Samples must be a minimum of 5 hours apart.

Part 2

Patients Randomized to G1T38 + Osimertinib

Sparse blood sampling for population PK analysis of G1T38 will be collected during Part 2 for patients randomized to G1T38 + osimertinib. The goal of this sparse sampling is to obtain G1T38 steady-state blood samples from participating patients at the following time points/intervals relative to G1T38 dosing: predose and at 1 to 3, 3 to 6, and 6 to 8 hours postdose. Each participating patient should have a total of 4 blood samples taken, 1 during each time point/interval (see Table 10-2).

On Cycle 1 Day 15, patients shall be instructed to not take their G1T38 dose at home as the dose will be administered in the clinic following collection of the predose blood sample. In addition, on Cycle 1 Day 15, a blood sample shall be obtained at 1 to 3 hours postdose. It is strongly encouraged that the site contact the patient via telephone prior to the Cycle 1 Day 15 visit to remind the patient not to take the morning dose of G1T38.

On Cycle 1 Day 22, a blood sample shall be obtained 3 to 6 hours postdose. On Cycle 2 Day 1, a blood sample shall be obtained 6 to 8 hours postdose. It is anticipated that patients will self-administer G1T38 at a range of times during the day and that clinic visits may occur at any time throughout the day during normal business hours. The investigator is encouraged to work with the patient to schedule visits at an appropriate time of day in order to obtain the blood samples during the specified time intervals.

Table 10-3 Part 2 Blood Sampling Scheme for G1T38 Population PK Analysis

Sample	1	2	3	4
Cycle/Day	Cycle 1	Day 15	Cycle 1 Day 22	Cycle 2 Day 1
Time point	Predose	1-3 hours postdose	3-6 hours postdose	6-8 hours postdose
Notes	G1T38 admini	stered in clinic		

10.5.2. Pharmacokinetic Parameters

[figure not shown]

Table 10-4 Pharmacokinetic Parameters for G1T38

C _{max}	The observed peak plasma concentration determined from the plasma concentration versus time data
T _{max}	The time to reach the observed peak plasma concentration from the plasma concentration versus time data
$\lambda_{\rm z}$	Terminal phase rate constant, determined by linear regression of at least 3 points on the terminal phase of the log-linear plasma concentration-time curve.
t _{1/2}	Terminal half-life, defined as 0.693 divided by $\lambda_{\rm z}$
AUC _{last}	Area under the concentration-time curve from time zero to the last quantifiable concentration using the linear-up log-down trapezoidal rule.
AUC _{inf}	Area under the concentration-time curve from time zero extrapolated to infinity using the linear-up log-down trapezoidal rule.
CL/F	Clearance after oral administration, calculated as: $CL/F = Dose/AUC_{0-\infty} (G1T38 \text{ only})$
Vz/F	Volume of distribution in the terminal elimination phase, calculated as: $Vz/F = (CL/F)/\lambda z \; (G1T38 \; only)$
M/P Ratio	Metabolite to parent ratio calculated as G1T30 _{AUCinf} /G1T38 _{AUCinf}

10.6. Safety Assessments

Safety evaluations will begin after the first dose of any study drug and continue throughout the study. Safety evaluations will include monitoring of AEs, vital signs measurements, physical examinations, ECGs, echocardiograms/ multigated acquisition (MUGA) scans, ophthalmic exams, and clinical laboratory assessments.

Toxicity will be graded by the investigators using the NCI CTCAE, Version 4.03.

10.6.1. Adverse Events and Serious Adverse Events

Adverse events are captured following the first dose of study drug. All AEs should be reported within 30 days of the last dose of study drug, and followed until they are resolved, have returned to baseline, or it is deemed that further recovery is unlikely.

10.6.1.1. Definition of Adverse Event

An AE is defined as any untoward medical occurrence in a patient administered a medicinal product that does not necessarily have a causal relationship with this treatment. An AE can, therefore, be any unfavorable and unintended sign (including an abnormal laboratory finding), symptom, or disease temporally associated with the use of a medicinal (investigational) product, whether or not related to the study (investigational) product.

Adverse events include the following:

- All suspected study drug-related adverse events
- All reactions from medication overdose, abuse, withdrawal, sensitivity, or toxicity
- Apparently unrelated illnesses, including the worsening of a pre-existing illness (see pre-existing conditions below)
- Injury or accidents (Note that if a medical condition is known to have caused the injury or accident [eg, a fall secondary to dizziness], the medical condition [dizziness] and the accident [fall] should be reported as 2 separate AEs). The outcome of the accident (eg, hip fracture secondary to the fall) should be recorded under comments.
- Abnormalities in physiological testing or physical examination (findings that require clinical intervention or further investigation beyond ordering a repeat [confirmatory] test)
- Laboratory abnormalities that are clinically significant and require clinical intervention or further investigation (beyond ordering a repeat [confirmatory] test) unless they are associated with an already reported clinical event. Laboratory abnormalities associated with a clinical event (eg, elevated liver enzymes in a patient with jaundice) should be described under comments on the report of the clinical event rather than listed as a separate AE.

An AE does not include:

- Medical or surgical procedures (eg, surgery, endoscopy, tooth extraction, transfusion); the condition that leads to the procedure may be an AE
- Pre-existing diseases or conditions present or detected at the start of the study that do not worsen
- Situations where an untoward medical occurrence has not occurred (eg, hospitalization for elective surgery, social, and/or convenience admissions)
- Overdose of either study drug or concomitant medication without any signs or symptoms
- Progression of the malignancy under study, including signs and symptoms progression
 - Disease progression can be considered as a worsening of a patient's condition attributable to the disease for which the investigational product is being studied. It may be an increase in the severity of the disease under study and/or increases in the symptoms of the disease. The development of new, or progression of existing metastasis to the primary cancer under study should be considered as disease progression and not an AE
- Hospitalization due to signs and symptoms of disease progression

An unexpected AE is any AE that is not identified in nature, severity, or frequency in the current IB or product information. The sponsor or designee shall be responsible for determining expectedness; this is not the responsibility of the investigator.

• An Adverse Drug Reaction (ADR) is defined as an AE that is caused by a drug (aka drug-related AE). An unexpected ADR is an adverse reaction, the nature or severity of which is not consistent with the applicable product information (eg, IB for an unapproved investigational medicinal product). All noxious and unintended responses to a medicinal product related to any dose should be considered ADRs. The phrase "responses to a medicinal product" means that a causal relationship between a medicinal product and an AE is at least a reasonable possibility, ie, the relationship cannot be ruled out. All serious and unexpected ADRs will have expedited reporting to the regulatory agencies following the ICH requirements

It is the responsibility of the investigator to document all AEs that occur during the study and every effort should be made to adequately capture all possible AEs. Patients should be encouraged to report AEs spontaneously or in response to general, nondirected questioning. Adverse events should be reported on the appropriate page of the eCRF.

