10.6.1.2. Definition of Serious Adverse Event

The International Council for Harmonisation (ICH) topic E2A on Clinical Safety Data Management, Definitions and Standards for Expedited Reporting defines an SAE as any untoward medical occurrence that at any dose:

- Results in death
- Is life threatening

 NOTE: The term "life threatening" in the definition of "serious" refers to an event in which the patient was at risk of death at the time of the event; it does not refer to an event which hypothetically might have caused death if it were more severe.
- Requires inpatient hospitalization or prolongation of existing hospitalization
- Results in persistent or significant disability/incapacity
- Is a congenital anomaly/birth defect

Medical and scientific judgment should be exercised in deciding whether expedited reporting (see Section 10.6.1.9) is appropriate in other situations, such as important medical events that may not be immediately life threatening or result in death or hospitalization but may jeopardize the patient or may require intervention to prevent one of the other outcomes listed in the definition above. These should also usually be considered serious. Examples of such events are intensive treatment in an emergency room or at home for allergic bronchospasm; blood dyscrasias or convulsions that do not result in hospitalization; or development of drug dependency or drug abuse.

To ensure there is no confusion or misunderstanding of the difference between the terms "serious" and "severe", the following note of clarification is provided:

The term "severe" is often used to describe the intensity (severity) of a specific event (as in mild, moderate, or severe myocardial infarction); the event itself, however, may be of

relatively minor medical significance (such as severe headache). This is not the same as "serious," which is based on patient/event outcome or action criteria usually associated with events that pose a threat to a patient's life or functioning. Seriousness (not severity) serves as a guide for defining regulatory reporting obligations.

Hy's Law

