5.2.10. Safety Analyses (Part 1)

Adverse Events

Details for imputing missing or partial start dates of AEs are described in [Section 4.2.1](#).

AE overall summary tables will be presented for TEAEs only and will include the following:

- Number of TEAEs (all events are counted)

And, patients with any,

- TEAEs
- Grade 3 or higher TEAEs
- TEAEs related to either G1T38 or Osimertinib
 - G1T38-related TEAEs
 - Osimertinib-related TEAEs
 - G1T38 and Osimertinib-related TEAEs
- Grade 3 or higher TEAEs related to either G1T38 or Osimertinib
 - Grade 3 or higher G1T38-related TEAEs
 - Grade 3 or higher Osimertinib-related TEAEs
 - Grade 3 or higher G1T38 and Osimertinib-related TEAEs
- Serious TEAEs

G1 Therapeutics, Inc.
Clinical Study Protocol G1T38-03
Statistical Analysis Plan

- Grade 5 TEAEs or TEAEs with fatal outcome (death)
- Serious TEAEs related to either G1T38 or Osimertinib
 - G1T38-related serious TEAEs
 - Osimertinib-related serious TEAEs
 - G1T38 and Osimertinib-related serious TEAEs
- TEAE leading to G1T38 dose reduction
- TEAEs leading to discontinuation of either G1T38 or osimertinib
 - TEAEs leading to discontinuation of G1T38
 - TEAEs leading to discontinuation of Osimertinib
 - TEAEs leading to discontinuation of G1T38 and Osimertinib

TEAEs will be summarized in descending frequency of all dose levels combined as follows:

- TEAEs by SOC and PT (without collapsed terms);
- Serious TEAEs by SOC and PT;
- TEAEs by PT and by CTCAE grade;
- G1T38-related TEAEs by PT and by CTCAE grade;
- Osimertinib-related TEAEs by PT and by CTCAE grade;
- G1T38-related and Osimertinib-related TEAEs by PT and by CTCAE grade;
- G1T38-related or Osimertinib-related TEAEs by PT and by CTCAE grade;
- G1T38-related TEAEs by SOC and PT;
- Osimertinib-related TEAEs by SOC and PT;
- G1T38-related and Osimertinib-related TEAEs by SOC and PT;
- G1T38-related or Osimertinib-related TEAEs by SOC and PT;
- G1T38-related serious TEAEs by SOC and PT ;
- Osimertinib-related serious TEAEs by SOC and PT;
- G1T38-related and Osimertinib-related serious TEAEs by SOC and PT;
- G1T38-related or Osimertinib-related serious TEAEs by SOC and PT;
- Grade 3 or higher TEAEs by PT;
- Grade 3 or higher G1T38-related TEAEs by PT;

G1 Therapeutics, Inc.
Clinical Study Protocol G1T38-03
Statistical Analysis Plan

- Grade 3 or higher Osimertinib-related TEAEs by PT;
- G1T38 or Osimertinib-related, Grade 3 or higher TEAEs by PT;

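### The accident rule in Protocol 10.6.1.1 contradicts the protocol's own AE definition and can hide an injury's preferred term, grade, causality and duration behind the record for the fall.

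*Protocol*

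**What the plan says.** Three parts of Protocol 10.6.1.1 bear on this point.

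- The general definition: "An AE is defined as any untoward medical occurrence in a patient administered a medicinal product", whether or not it is related to treatment.
- The list of things that count as AEs, which includes a bullet that opens "Injury or accidents (Note that if a medical condition is known to have caused the injury or accident". In its example, "the medical condition [dizziness] and the accident [fall] should be reported as 2 separate AEs".
- The sentence that closes the same bullet: "The outcome of the accident (eg, hip fracture secondary to the fall) should be recorded under comments".

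Protocol 10.6.1.2 applies the seriousness criteria to untoward occurrences in general. Among the criteria is "Requires inpatient hospitalization or prolongation of existing hospitalization". It makes no exception for the results of accidents.

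On the analysis side, SAP 4.2.1 classifies AEs by system organ class and preferred term. SAP 5.2.10 builds its tables from those records, among them "Grade 3 or higher TEAEs by PT" and a table of serious events by class and term.

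**The concern.** The example contains three unwanted occurrences: dizziness, a fall and a hip fracture. The first two become AE records. The third, which is the most harmful, is sent to a comments field. That is hard to square with a definition wide enough to cover a fracture, or with a bullet that names injury as an AE.

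What is at stake is the accuracy of safety capture, and safety and tolerability are primary objectives of Part 1 (SAP 2.1). A site that follows the specific sentence enters two records. A site that follows the general definition enters three. The same clinical episode can then appear under different preferred terms and grades depending on the site, and in small dose cohorts a single event is visible.

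**Working it through.** The plan states no figure on this point, so there is nothing to reproduce. The check is to trace the protocol's own example through each step that produces the safety tables.

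**What each step acts on**

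- Severity grading (Protocol 10.6.1.3): AEs, by CTCAE 4.03.
- Causality (10.6.1.4): each AE, separately for each study drug.
- Outcome and follow-up (10.6.1.5, 10.6.1.10): AEs.
- MedDRA coding (10.6.1.8): the investigator's AE verbatim terms.
- Duration (SAP 4.2.1): AE stop date minus AE onset date plus 1.
- Missing grade or causality (SAP 4.2.1): set to Grade 3 or to related, but only where an AE record exists.
- Tables (SAP 5.2.10): AE records, by term and grade.

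None of these steps refers to comments.

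**The example under the rule and under the general definition**

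| | Rule followed literally | Injury entered as its own AE |
|---|---|---|
| AE records | dizziness, fall = 2 | dizziness, fall, fracture = 3 |
| Patients in the any-TEAE row | 1 | 1 |
| Preferred term for the fracture | none | yes |
| Grade, causality and duration of the fracture | none | yes |
| Serious-TEAE table | present if the fall (or dizziness) is flagged serious | also present under the fracture if it is serious |

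**Grade 3 or higher.** Let gD, gF and gI be the grades of the dizziness, the fall and the injury. Under the rule the patient is counted if max(gD, gF) is at least 3. With the injury recorded, the condition is max(gD, gF, gI) at least 3. The two differ only when gI is 3 or more and both gD and gF are below 3. Whether that can happen depends on whether a fall is graded by its consequence. The documents do not say; Protocol Appendix 1 only links to the CTCAE.

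**Duration.** A fall is over at once, while a fracture can last for months. If only the fall has onset and stop dates, the derived duration is that of the fall.

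**DLTs.** Protocol 6.1.1.2 and SAP 4.2.2 define DLTs as drug-related AEs, including nonhematologic toxicity of Grade 3 or higher. From Cohort 2 on, 0 DLTs in 3 patients allows escalation and 1 in 3 leads to 3 more patients at the same level (Protocol 6.1.1.1). For the comments rule to change that count, four things must coincide: the injury is Grade 3 or higher, it is judged drug-related, it falls between Cycle 1 Day -16 and Day 28, and neither the investigator nor the SMC acts on it.

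**The case against.** The strongest reply is that the sentence does not forbid a separate record for the injury. The bullet itself lists injury as an AE. The laboratory bullet in the same section shows how the protocol words an exclusion: such findings "should be described under comments on the report of the clinical event rather than listed as a separate AE". The accident bullet has no such words. The section also requires that "every effort should be made to adequately capture all possible AEs". On this reading the comment merely describes the fall and a site may still enter the fracture. That reading is available, but it is not the natural one. The example counts two AEs and gives the fracture a different place, and a site that does as told would stop there.

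A reader might infer something stronger: that a serious or Grade 3 or higher injury is never coded or graded and drops out of the AE tables. The documents do not support that. The fall remains a coded and graded AE. A hospitalised injury still meets the seriousness definition in 10.6.1.2, goes on the SAE form (10.6.1.7), must be entered within 24 hours (10.6.1.9) and falls under full source verification of SAEs (15.1).

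A reader might also infer that a DLT would be missed. Investigators assess each patient for toxicity (6.1.1.2) and the SMC reviews all safety data for the DLT period (6.1.1), so DLT decisions do not rest on the SAP tables. A miss is possible, not shown.

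Finally, SAP 5.1.1 lists all data for enrolled patients, and the AE listing in 5.2.10 names its fields without claiming to be complete. The comment text may therefore survive in a listing. That preserves the information but does not give it a term or a grade. The eCRF and its completion guide are not among the documents and may already deal with this.

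**Conclusion.** The point holds in a narrow form. The accident rule conflicts with the AE definition and with its own bullet. Followed literally, it removes the injury's own preferred term, grade, causality and duration. It does not remove the patient from the any-TEAE table or the event from SAE reporting. Its effect on the Grade 3 or higher table is conditional on how the fall is graded.

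The size is small. Part 2 will not be conducted (SAP 1), Part 1 has at most 36 patients (SAP 2.3), and its analysis is descriptive without formal tests (SAP 5.1.1). The rule touches only injuries that result from accidents. The documents give no frequency for these, so the number of patients affected cannot be estimated; any rate would be a guess, and a rate for injurious accidents in general would say nothing about drug-related Grade 3 injuries within the DLT period.

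The conclusion assumes that sites follow the sentence as written and that no eCRF guidance overrides it. It is a worthwhile clarification, not a threat to the trial's conclusions.

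**What to change.** Replace the closing sentence of the accident bullet with one to this effect: an injury that itself meets the AE definition is recorded as its own AE, graded by CTCAE, assessed for seriousness and for causality to each study drug, and linked to the records for the accident and its medical cause. Carry the same wording into the eCRF completion guide. Before database lock, query the comments on existing accident AEs and enter any injury found there under the new rule.

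The cost is one sentence and a short data query. The number of TEAEs rises slightly, by one for an episode like the protocol's example (from 2 to 3), and one episode is then counted under more than one preferred term. The link between records lets a reader see that these belong together. The change concerns recording only and leaves patient management as it is.

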10.6.1.2. Definition of Serious Adverse Event

The International Council for Harmonisation (ICH) topic E2A on Clinical Safety Data Management, Definitions and Standards for Expedited Reporting defines an SAE as any untoward medical occurrence that at any dose:

- Results in death
- Is life threatening

 NOTE: The term "life threatening" in the definition of "serious" refers to an event in which the patient was at risk of death at the time of the event; it does not refer to an event which hypothetically might have caused death if it were more severe.
- Requires inpatient hospitalization or prolongation of existing hospitalization
- Results in persistent or significant disability/incapacity
- Is a congenital anomaly/birth defect

Medical and scientific judgment should be exercised in deciding whether expedited reporting (see Section 10.6.1.9) is appropriate in other situations, such as important medical events that may not be immediately life threatening or result in death or hospitalization but may jeopardize the patient or may require intervention to prevent one of the other outcomes listed in the definition above. These should also usually be considered serious. Examples of such events are intensive treatment in an emergency room or at home for allergic bronchospasm; blood dyscrasias or convulsions that do not result in hospitalization; or development of drug dependency or drug abuse.

To ensure there is no confusion or misunderstanding of the difference between the terms "serious" and "severe", the following note of clarification is provided:

The term "severe" is often used to describe the intensity (severity) of a specific event (as in mild, moderate, or severe myocardial infarction); the event itself, however, may be of

relatively minor medical significance (such as severe headache). This is not the same as "serious," which is based on patient/event outcome or action criteria usually associated with events that pose a threat to a patient's life or functioning. Seriousness (not severity) serves as a guide for defining regulatory reporting obligations.

Hy's Law

Prompt reporting (via the SAE expedited reporting system) of cases meeting Hy's law criteria (AST or ALT \geq 3 \times ULN and total bilirubin \geq 2 \times ULN) is required for compliance with regulatory guidelines. The investigator is responsible for, without delay, determining whether a patient meets potential Hy's law criteria. Any patient with liver function test abnormalities meeting Hy's Law criteria must have all study drugs permanently discontinued.

Additional Reporting Requirements for Osimertinib

The following will also be reported to pharmacovigilance: any osimertinib overdose; if a patient taking osimertinib begins lactating; or if a male patient taking osimertinib fathers a child during the treatment period, including the Post-Treatment Follow-up visit. If these events also meet the criteria to be considered an SAE, they shall be reported as such.

Handling of Deaths

All deaths that occur during the study, or within the follow-up period after the administration of the last dose of investigational product, should be reported as described below.

Death, which is unequivocally due to disease progression, should be communicated to the study monitor at the next monitoring visit and should be documented in the eCRF module, but should not be reported as a SAE during the study

Where death is not clearly due to disease progression, the AE causing the death should be reported to the study monitor as an SAE within 24 hours. The report should contain a comment regarding the co-involvement of progression of disease, if appropriate, and should assign a single primary cause of death together with any contributory causes.

Deaths with an unknown cause should always be reported as a SAE but every effort should be made to establish a cause of death. A postmortem may be helpful in the assessment of the cause of death, and if performed, a copy of the post-mortem results (with translation of important parts into English) shall be reported, if possible, to the sponsor.

